Change from Baseline to Weeks 104 and 208 in CSF biomarkers (i.e., CSF Weeks 104 and 208 only), including CXCL13, BAFF (B cell activating factor), TNF, IL-6, IL-10, IL-17, interferon-gamma, IL-4, IL-23, IL-8, soluble CD27 (sCD27), genetic risk factors (HLA-DRB1*15:01) or other emerging exploratory markers of disease biology as appropriate

Change from Baseline to Weeks 48, 104, and 208 in slowly evolving lesions (SEL)

Change from Baseline to Weeks 24, 48, 72, 104, 130, 156, 182 and 208 in peripheral blood immune cell population frequency and phenotype, including B cells, T cells and innate immune cells (monocyte, macrophage, neutrophils, natural killer cells, etc.)

Change from Baseline to Weeks 24, 48, 72, 104, 130, 156, 182 and 208 in peripheral blood biomarkers, including CXCL13, BAFF (B cell activating factor), TNF, IL-6, IL-10, IL-17, interferon-gamma, IL-4, IL-23, IL-8, soluble CD27 (sCD27), genetic risk factors (e.g., HLA-DRB1*15:01) or other emerging exploratory markers of disease biology as appropriate

Change from Baseline to Weeks 24, 48, 72, 104, 130, 156, 182 and 208 in patient reported outcomes, including quality of life, fatigue, depression, and disability, as measured by Neuro-QoL™

Change from Baseline to Weeks 24, 48, 72, 104, 130, 156, 182 and 208 in cognitive function and information processing speed as measured by symbol digit modality test (SDMT)

Correlation between changes in compartment-specific biomarkers of disease biology with radiologic and/or clinical disease outcomes

Correlation between changes in patient reported outcomes, including SDMT, and radiologic and/or clinical disease outcomes

Correlation between changes in compartment-specific immune cell subsets with radiologic and/or clinical disease outcomes.

Correlation between changes in NfL levels and radiologic and/or clinical disease outcomes

Correlation between changes in CSF abnormalities (OCB and IgG index) and radiologic and/or clinical disease outcomes

SAFETY OBJECTIVES

The safety objectives for this study are to evaluate the safety of ocrelizumab compared with placebo on the basis of the following endpoints:

Nature, frequency, severity, and timing of adverse events

Vital signs, physical findings, and clinical laboratory results during and following study drug administration

Adverse events related to biomarker sample collection

STUDY DESIGN

DESCRIPTION OF THE STUDY

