Several measures will be taken to ensure the safety of patients participating in this study. Eligibility criteria have been designed to exclude patients at higher risk for toxicities. Patients will undergo safety monitoring during the study, including assessment of the nature, frequency, and severity of adverse events. In addition, guidelines for managing adverse events, including criteria for dosage modification and treatment interruption or discontinuation, are provided below.

Risks Associated with Ocrelizumab

Important, identified, and potential risks associated with ocrelizumab are described in the approved risk management plan, and provided below. Please refer to the most recent version of the Ocrelizumab Investigator's Brochure for updates on risks associated with ocrelizumab treatment.

Identified Risks and Adverse Drug Reactions

Infusion-Related Reactions

All CD20-depleting agents administered via the intravenous route, including ocrelizumab, have been associated with acute IRRs. Following the approved administration regimen (which includes the use of premedication prior to treatment with ocrelizumab to reduce frequency and severity of IRRs), symptoms of IRRs may occur during any ocrelizumab infusion, but have been more frequently reported during the first infusion. Physicians should alert patients that IRRs can occur within 24 hours of the infusion. Across the RMS and PPMS trials, symptoms associated with IRRs included, but are not limited to the following: pruritus, rash, urticaria, erythema, bronchospasms, throat irritation, oropharyngeal pain, dyspnea, pharyngeal or laryngeal edema, flushing, hypotension, pyrexia, fatigue, headache, dizziness, nausea, tachycardia, and anaphylaxis.

Patients should be observed for at least 1 hour after the completion of the infusion for any symptom of IRR. Patients will be informed about delayed post-infusion symptoms and instructed to contact the study physician if he or she develops such symptoms.

Hypotension, as a symptom of IRR, may occur during ocrelizumab infusions. Therefore, withholding of antihypertensive treatments should be considered for 12 hours prior to and throughout each ocrelizumab infusion.

For further guidance on how to manage IRRs please refer to the current Ocrelizumab Investigator's Brochure.

Infections

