The above examples of dose interruption and slowing (for mild/moderate and severe IRRs) will result in a change in the infusion rate and increase the total duration of the infusion but not the total dose.

SAFETY PARAMETERS AND DEFINITIONS

Safety assessments will consist of monitoring and reporting adverse events (AEs) and serious adverse events (SAEs) per protocol. This includes all events of death and any study-specific issue of concern.

Adverse Events

An AE is any unfavorable and unintended sign (including an abnormal laboratory finding), symptom, or disease temporally associated with the use of an investigational medicinal product (IMP) or other protocol-imposed intervention, regardless of attribution.

This includes the following:

AEs not previously observed in the subject that emerge during the protocol-specified AE reporting period, including signs or symptoms associated with multiple sclerosis that were not present prior to the AE reporting period.

Complications that occur as a result of protocol-mandated interventions (e.g., invasive procedures such as cardiac catheterizations).

If applicable, AEs that occur prior to assignment of study treatment associated with medication washout, no treatment run-in, or other protocol-mandated intervention.

Preexisting medical conditions (other than the condition being studied) judged by the investigator to have worsened in severity or frequency or changed in character during the protocol-specified AE reporting period.

Serious Adverse Events

An AE should be classified as an SAE if the following criteria are met:

It results in death (i.e., the AE actually causes or leads to death).

It is life threatening (i.e., the AE, in the view of the investigator, places the subject at immediate risk of death. It does not include an AE that, had it occurred in a more severe form, might have caused death.).

It requires or prolongs inpatient hospitalization.

It results in persistent or significant disability/incapacity (i.e., the AE results in substantial disruption of the subject's ability to conduct normal life functions).

It results in a congenital anomaly/birth defect in a neonate/infant born to a mother exposed to the IMP.

It is considered a significant medical event by the investigator based on medical judgment (e.g., may jeopardize the subject or may require medical/surgical intervention to prevent one of the outcomes listed above).

Adverse Events of Special Interest

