All AEs and SAEs whether volunteered by the subject, discovered by study personnel during questioning, or detected through physical examination, laboratory test, or other means will be reported appropriately. Each reported AE or SAE will be described by its duration (i.e., start and end dates), regulatory seriousness criteria if applicable, suspected relationship to OCRELIZUMAB (see following guidance), and actions taken.

To ensure consistency of AE and SAE causality assessments, investigators should apply the following general guideline:

Yes

There is a plausible temporal relationship between the onset of the AE and administration of OCRELIZUMAB, and the AE cannot be readily explained by the subject's clinical state, intercurrent illness, or concomitant therapies; and/or the AE follows a known pattern of response to OCRELIZUMAB; and/or the AE abates or resolves upon discontinuation of OCRELIZUMAB or dose reduction and, if applicable, reappears upon re-challenge.

No

Evidence exists that the AE has an etiology other than OCRELIZUMAB (e.g., preexisting medical condition, underlying disease, intercurrent illness, or concomitant medication); and/or the AE has no plausible temporal relationship to OCRELIZUMAB administration (e.g., cancer diagnosed 2 days after first dose of OCRELIZUMAB).

Expected adverse events are those adverse events that are listed or characterized in the Package Insert (P.I) or current Investigator Brochure (I.B).

Unexpected adverse events are those not listed in the P.I. or current I.B or not identified. This includes adverse events for which the specificity or severity is not consistent with the description in the P.I. or I.B. For example, under this definition, hepatic necrosis would be unexpected if the P.I. or I.B. only referred to elevated hepatic enzymes or hepatitis.

PROCEDURES FOR ELICITING, RECORDING, AND REPORTING ADVERSE EVENTS

Eliciting Adverse Event Information

A consistent methodology of non-directive questioning should be adopted. Examples of non-directive questions include the following:

"How have you felt since your last clinic visit?"

"Have you had any new or changed health problems since you were last here?"

Specific Instructions for Recording Adverse Events

Investigators should use correct medical terminology/concepts when reporting AEs or SAEs. Avoid colloquialisms and abbreviations.

Diagnosis versus Signs and Symptoms

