At the end of the study, a final cumulative Case Transmission Verification report will be sent to Genentech.

Reporting Requirements For Adverse Events Originating From Patient Reported Outcomes

Although sites are not expected to review the PRO data, if physician/study personnel become aware of a potential adverse event during site review of the PRO questionnaire data, he/she will determine whether the criteria for an adverse event have been met and, if so, these must be reported using the Adverse Event and Special Situation Reporting Form or MedWatch form.

MedWatch 3500A Reporting Guidelines

In addition to completing appropriate patient demographic (Section A) and suspect medication information (Section C & D), the report should include the following information within the Event Description (Section B.5) of the MedWatch 3500A form:

Protocol number and title description

Description of event, severity, treatment, and outcome if known

Supportive laboratory results and diagnostics (Section B.6)

Investigator's assessment of the relationship of the adverse event to each investigational product and suspect medication

Follow-up Information

Additional information may be added to a previously submitted report by any of the following methods:

Adding to the original MedWatch 3500A report and submitting it as follow-up

Adding supplemental summary information and submitting it as follow-up with the original MedWatch 3500A form

Summarizing new information and faxing it with a cover letter including patient identifiers (i.e. D.O.B. initial, patient number), protocol description and number, if assigned, brief adverse event description, and notation that additional or follow-up information is being submitted (The patient identifiers are important so that the new information is added to the correct initial report)

MedWatch 3500A (Mandatory Reporting) form is available at
<https://www.fda.gov/media/69876/download>

Reporting to Regulatory Authorities, Ethics Committees and Investigators

Yale University, as the Sponsor of the Study, will be responsible for the expedited reporting of safety reports originating from the Study to the Regulatory Authorities (FDA) where it has filed a clinical trial approval, in compliance with local regulations.

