collected on the same day as the ocrelizumab infusion, the blood samples should be collected prior to ocrelizumab administration. Blood sample collection may precede ocrelizumab administration by up to 4 weeks. Leftover biological samples will be stored by the central laboratory for later biomarker use. Please refer to the laboratory manual for additional details on laboratory assessments and sample handling.

ⁿ To be obtained/Performed before administration of ocrelizumab (i.e., pre-dose). Premedication with methylprednisolone and antihistamines should be given in accordance to the guidance provided in the USPI.

^o The first dose of study drug will be administered as two 300 mg IV infusions given 14 days apart. For the subsequent doses, study drug will be administered as a single 600 mg IV infusion at Weeks 24 and 48. A minimum interval of 22 weeks must be maintained between each 600 mg dose of study drug.

^p LP is required at baseline for subjects who have not previously had CSF analysis or who do not have access to source documentation (including oligoclonal banding testing) for prior CSF analysis. LP is optional at baseline for subjects who have previously had CSF analysis and have appropriate source documentation. LP is always optional at Weeks 104, 208, and unscheduled visits (in case of a clinical neurologic event), at the investigator's discretion. Local lab testing for CSF includes protein, cell count/differential, and oligoclonal banding. CSF oligoclonal banding results must be available prior to randomization and study drug administration. Baseline CSF may be collected up to 4 weeks prior to administration of study drug. If MRI and CSF are performed on the same day, MRI should precede the collection of the CSF specimen and study drug infusion, and the CSF specimen collection should precede the study drug infusion. Blood biomarker samples should be collected as close as possible in time to the CSF sample, which may be prior to study drug administration by up to 4 weeks.

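### A safety endpoint counts adverse events related to biomarker sampling, but the protocol specifies causality only against drugs and defines no sampling-related summary

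*Combined protocol and SAP*

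**What the plan says.** **Endpoint.** The Safety Objectives list three safety endpoints. The third is "Adverse events related to biomarker sample collection".

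**Definition of an adverse event (Section 5.2, Adverse Events).** An event counts if it is associated in time with the product "or other protocol-imposed intervention, regardless of attribution". The list of inclusions names "Complications that occur as a result of protocol-mandated interventions (e.g., invasive procedures such as cardiac catheterizations", and it also takes in events before treatment assignment that are tied to a mandated intervention.

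**Attributes recorded (Section 5.3.2).** Each event is described by duration, seriousness where relevant, and "suspected relationship to OCRELIZUMAB (see following guidance), and actions taken". The guidance that follows is a single Yes/No for ocrelizumab. One ground for No is "Evidence exists that the AE has an etiology other than OCRELIZUMAB (e.g., preexisting medical condition, underlying disease, intercurrent illness, or concomitant medication"; the other is implausible timing.

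**MedWatch 3500A Reporting Guidelines.** The relationship item is "Investigator's assessment of the relationship of the adverse event to each investigational product and suspect medication".

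**Reporting period.** Section 5.3.1 starts it at initiation of treatment and ends it 24 weeks after the last administration, or at discontinuation if earlier. After that, only serious events attributed to study treatment are reported. Appendix 1, footnote u, instead has adverse events reported for the whole study.

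**Analysis (Section 6.5).** Events starting on or after the first dose are summarised by mapped term, thesaurus level and grade. No summary is planned for sampling-related events.

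**The concern.** An endpoint defined by the words related to needs a causality judgement, and someone has to record it. The only judgement specified concerns the drug. A complication of lumbar puncture that is correctly judged unrelated to ocrelizumab receives the same code as an unrelated cold or a sports injury.

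The endpoint matters in this trial. Participants have no symptoms of MS. Lumbar puncture is required at baseline for anyone without documented earlier CSF results, and it is offered again at Weeks 104 and 208, with blood and gingival sampling at most visits. Harm from sampling is what the endpoint exists to report. A later analysis plan can add a table, but it cannot recover a judgement that investigators were never asked to make.

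**Working it through.** The plan states no figure to reproduce. The check is a comparison of sections, plus simple arithmetic on weeks.

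**Step 1. What the endpoint needs against what is specified.**

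| Needed to derive the endpoint | Specified? | Where |
|---|---|---|
| Procedure complications count as adverse events | Yes | Section 5.2 definition |
| Start and end dates | Yes | Section 5.3.2 |
| Diagnosis rather than symptoms, when known | Yes | Diagnosis versus Signs and Symptoms |
| Relationship to sample collection | No | 5.3.2: ocrelizumab only; MedWatch: products and medications only |
| Summary of sampling-related events | No | Section 6.5 |

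**Step 2. A puncture complication under the guidance.** If the investigator blames the puncture, the natural answer is No, and the event joins all other unrelated events. The examples given for No do not include study procedures. The timing ground for Yes also requires that the event is not readily explained by clinical state, intercurrent illness or concomitant therapy; study procedures are missing from that list too. A match to a known ocrelizumab pattern can support Yes on its own.

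**Step 3. The reporting window against the sampling schedule.** The last scheduled infusion is at Week 48, so the Section 5.3.1 window runs from Week 0 to Week 48 + 24 = Week 72.

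| Sampling | Position relative to Week 0–72 |
|---|---|
| Baseline CSF, blood, swab | Up to 4 weeks before it opens |
| Blood and swab, Weeks 24 and 48 | Inside |
| Blood and swab, Week 72 | At the edge (72 − 72 = 0) |
| Puncture, Week 104 | 104 − 72 = 32 weeks after it closes |
| Puncture, Week 208 | 208 − 72 = 136 weeks after it closes |

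All three scheduled punctures can fall outside the window. Once it has closed, even a serious complication attributed to the puncture falls outside Section 5.3.1, because only serious events attributed to study treatment are still reported. Under Appendix 1, footnote u, every sampling time is covered. The two rules conflict.

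The Section 6.5 restriction acts separately: an event that starts after baseline sampling but before the first dose is left out of the summaries even if it was recorded.

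**Step 4. How far term and timing can substitute.** A recognised post-puncture headache should be entered as that diagnosis and could be found. A headache recorded only as a symptom is harder to place. The infusion-reaction symptoms in the risk section include "hypotension, pyrexia, fatigue, headache, dizziness, nausea, tachycardia, and anaphylaxis", and headache and nausea are also listed antihistamine effects. Appendix 1, footnote p, provides for both procedures on one day, in that "the CSF specimen collection should precede the study drug infusion". The approximation is therefore usable for some events and ambiguous for others.

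**The case against.** The strongest reply is that the list in Section 5.3.2 is not closed. It omits severity, which is nevertheless graded under a later heading, so the absence of an item there does not prove that it is not collected. The eCRF is not among the documents. The heading on assessment of causality in Section 5.4 shows no text beneath it, which may be a loss in conversion, and full analysis details are deferred to a SAP. This stands as a limit on certainty. It does not remove the point: nothing available requires the attribution, and the protocol should.

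Four stronger readings are tempting, and the documents do not support them.

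- A reader might infer that the endpoint has no data behind it or cannot be computed. The definition in Section 5.2, the recorded dates, the diagnosis rule and Appendix 1 all mean that relevant events can be in the database and can partly be identified.
- A reader might infer that same-day sampling and infusion blurs attribution for every required baseline puncture. Oligoclonal band results must be available before randomization and before study drug, so a required puncture comes before the infusion by at least the laboratory turnaround. Same-day overlap is realistic mainly for optional baseline punctures in patients with earlier CSF results.
- A reader might infer that puncture events will often be called drug-related and so trigger code-breaking. Those steps need events that are both serious and unexpected, whereas the overlapping symptoms are ones the protocol already lists for ocrelizumab infusions. The later punctures come 104 − 48 = 56 and 208 − 48 = 160 weeks after the last scheduled infusion, where the implausible-timing ground readily gives No.
- A reader might extend the point to contrast MRI and premedication. Neither is biomarker sample collection, so both lie outside the stated endpoint.

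**Conclusion.** The point holds as a missing attribution and a missing analysis rule for one of three safety endpoints. As written, the endpoint can only be approximated from term and timing. The approximation is weakest for non-specific symptoms, and the Section 5.3.1 period and the first-dose restriction can remove events around all three scheduled punctures.

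Its size cannot be put as a number of events, because the documents give no puncture complication rate and no count of patients with earlier CSF results. Those exposed to a required puncture are the patients among approximately 100 without documented earlier CSF results; those exposed later are whoever consents at Weeks 104 and 208. The primary analysis is not touched.

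The conclusion assumes that the eCRF has no procedure-relationship field and that no other operational document requires one. If a field exists, what remains is to state it in the protocol, plan the table and reconcile the time windows.

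**What to change.** 1. In Section 5.3.2, and on the adverse event eCRF if it is not already there, add a yes/no item: related to study sample collection (lumbar puncture, blood draw, gingival swab), with the procedure specified.
2. Add study procedures to the alternative explanations in the causality guidance, under both Yes and No.
3. In Section 6.5, add a table of sampling-related adverse events by arm. For puncture events, use the number of lumbar punctures performed as the denominator. Include events after baseline sampling but before the first dose, and events after the Week 104 and 208 punctures.
4. Reconcile the Section 5.3.1 reporting period and the first-dose restriction in Section 6.5 with the Section 5.2 definition and Appendix 1, footnote u. Without this, the table in item 3 would be incomplete even with the new attribution.

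The cost is one extra question per adverse event for sites and one extra table. The change is best made early, because the judgement has to be recorded when the event is assessed.

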The primary efficacy objective for this study is to evaluate the treatment effect of ocrelizumab compared with placebo on delaying the time to development of new radiologic or clinical evidence of MS.

Primary Efficacy Endpoint:

Time to development of first new radiologic (e.g., new or enlarging T2 lesions, T1 gadolinium-enhancing lesions consistent with MS) or clinical evidence of MS (i.e., neurological event resulting from CNS demyelination, as evidenced by acute or progressive clinical syndrome consistent with MS).

A detailed description of the primary endpoints and estimands are provided in Section 6.4.1.

SECONDARY OBJECTIVE(S)

Secondary Efficacy Objective

The secondary objectives for this study are to understand the treatment effect of ocrelizumab compared with placebo on clinical, neuroimaging and serum neurofilament light (NfL) biomarkers that are associated with disease activity, and with the clinical response to ocrelizumab.

Secondary Efficacy Endpoints:

Cumulative number of new or enlarging T2 lesions identified at Weeks 48, 104 and 208

Change in T2-lesion volume from Baseline to Weeks 48, 104 and 208

Cumulative number of new T1 gadolinium-enhancing lesions identified at Weeks 48, 104 and 208

Change from Baseline to Weeks 48, 104 and 208 in total brain volume

Change from Baseline to Weeks 48, 104 and 208 in total spinal cord volume

Change from Baseline to Weeks 48, 104 and 208 in serum NfL (sNfL)

Exploratory Efficacy Objectives

The exploratory objectives for this study are to evaluate inflammatory, neurodegenerative, and exploratory biomarkers of disease activity in the blood and cerebrospinal fluid (CSF) and their correlations with radiologic, clinical and patient reported outcomes.

Exploratory Efficacy Endpoints:

Change from Baseline to Weeks 48, 104 and 208 in white matter volume, gray matter volume, and thalamic volume

Change from Baseline to Weeks 48, 104 and 208 in spinal cord white and gray matter volume

Change from Baseline to Week 104 and 208 in CSF immune cell populations frequency and phenotype

Change from Baseline to Week 104 and 208 in CSF NfL levels

Percent change in the presence of CSF oligoclonal bands (OCB) from Baseline to Weeks 104 and 208

Percent change in normalization of CSF IgG index from Baseline to Weeks 104 and 208

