The Parties shall follow their own procedures for adherence to AE reporting timelines.

Each Party shall monitor and, as applicable, request feedback from the other Party regarding AE report timeliness in accordance with its own procedures. The Parties agree to provide written responses in a timely manner to inquiries from the other Party regarding AE reports received outside the agreed upon Agreement timelines. If there is any detection of trends of increasing or persistent non-compliance to transmission timelines stipulated in this Agreement, both Parties agree to conduct ad hoc or institute a regular joint meeting to address the issue.

In case of concerns related to non-compliance of processes, other than exchange timelines, with this Agreement, the Parties will jointly discuss and collaborate on

clarifying and resolving the issues causing non-compliance. Every effort will be made by the non-compliant Party to solve the non-compliance issues and inform the other Party of the corrective and preventative actions taken.

Upon justified request, given sufficient notice of no less than sixty (60) calendar days, an audit under the provisions of this Agreement can be requested by either Party. The Parties will then discuss and agree in good faith upon the audit scope, agenda and execution of the audit. The requesting Party will bear the cost of the audit.

STATISTICAL CONSIDERATIONS

Unless otherwise specified, all baseline and efficacy analyses will be based on the intend-to-treat (ITT) population (defined as all randomized patients). The safety evaluable population will include all patients who received any amount of study drug. Unless otherwise specified, all baseline and efficacy analyses will use the ITT population as assigned by randomization. Safety analyses will be performed by treatment received.

The primary analysis will occur when the last randomized patient has reached 4 years and the specified number of new radiological or clinical evidence of MS has accrued as specified in Section 3.1.

All statistical hypotheses for the primary and secondary endpoints and treatment comparisons will be tested at the 5% significance level ($\alpha = 0.05$) against two-sided alternatives unless otherwise specified. The SAP will contain full details of the statistical analyses specified for this protocol.

DETERMINATION OF SAMPLE SIZE

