The purpose of this study is estimation and hypothesis testing regarding the effect of ocrelizumab on the time from baseline to radiological or clinical evidence of MS relative to placebo. P-values, point- and interval estimates of the true underlying hazard ratio will be obtained.

The sample size of this trial is based on testing the null hypothesis of no difference between the control and ocrelizumab arms. This study will enroll approximately 100 patients with an expected recruitment of over 2 years. The sample size of this study is driven by the primary efficacy analysis of radiological or clinical evidence of MS and the following assumptions:

A two-group test of equal times to radiological or clinical evidence of MS

Two-sided type I error = 0.05

33% of the patients in the control arm and 20% of patients in the ocrelizumab arm having radiological or clinical evidence of MS occurring by 4 years.

A final analysis is based on approximately 21 radiological or clinical events to have 80% power 10% annual dropout rate.

SUMMARIES OF CONDUCT OF STUDY

The number of patients who enroll, discontinue, or complete the study and ocrelizumab administration will be summarized. Reasons for premature study discontinuation and treatment discontinuation will be listed and summarized. Major protocol deviations, including violations of inclusion/exclusion criteria will also be listed and summarized.

SUMMARIES OF TREATMENT GROUP COMPARABILITY

Demographic and baseline characteristics (including age, sex, body mass index), medical history, and neurological examination will be summarized using means, standard deviations, medians, and ranges for continuous variables and proportions for categorical variables, as appropriate. MS disease history (duration since MS first symptom, duration since MS diagnosis), MS disease status (MS treatment naïve or experienced) will be summarized. The baseline measures of MRI, EDSS, or other important endpoints will also be tabulated. Summaries will be presented overall and by patient cohorts.

EFFICACY ANALYSES

The primary efficacy analysis population will consist of all randomized patients, with patients grouped according to their assigned treatment (i.e., the ITT population). All statistical hypotheses for the primary and secondary endpoints and treatment comparisons will be tested at the 5% significance level against two-sided alternative unless otherwise specified.

Primary Efficacy Endpoint

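### Up to 18 secondary comparisons are each tested at two-sided 5%, and the documents give no order, gate, key time point or adjustment

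*Combined protocol and SAP*

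**What the plan says.** The significance rule appears twice. The opening of Section 6 says "All statistical hypotheses for the primary and secondary endpoints and treatment comparisons will be tested at the 5% significance level", with two-sided alternatives. The Efficacy Analyses section repeats that these hypotheses are "tested at the 5% significance level against two-sided alternative unless otherwise specified". The opening of Section 6 also says "The SAP will contain full details of the statistical analyses specified for this protocol".

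Section 2.2.1 lists six secondary efficacy endpoints, each at three visits. The first reads "Cumulative number of new or enlarging T2 lesions identified at Weeks 48, 104 and 208". The other five use the same three visits and cover the volume of T2 lesions, the running count of enhancing T1 lesions, whole-brain volume, cord volume and serum neurofilament light.

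The Secondary Efficacy Endpoints part of Section 6.4 assigns the tests: a repeated-measures mixed model for each continuous change from baseline, and a count model such as negative binomial regression for the two lesion counts. It does not rank the endpoints, choose a visit, tie the tests to the primary result or adjust for their number.

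The Interim Analyses section contains the only statement about overall type I error. It provides for alpha spending if an unplanned interim look for superiority is triggered.

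**The concern.** As written, the rule gives each secondary comparison the same 5% threshold as the primary, without separating confirmatory from descriptive results. With six endpoints at three visits, the chance that at least one crosses the threshold with no true effect is well above 5%.

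What the trial may conclude is at stake. On the plan's own assumptions the primary test has low power (see the working), so a non-significant primary beside one or two nominally significant secondary results is a realistic outcome. New T2 lesions and gadolinium-enhancing lesions are also components of the primary endpoint, which would make it easy to put a secondary result in place of a failed primary. The text does not say how such a result should be described.

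**Working it through.** **Number of comparisons.** Section 2.2.1 gives 6 endpoints x 3 visits = 18. The documents never state 18 or say that each visit is a separate formal test, so 18 is an upper count. One test per endpoint would give 6.

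**The plan's own figures.** The documents state no family-wise error for the secondary endpoints, so there is none to reproduce. They do state a power for the primary, which bears on the importance of the point and on the cost of one remedy. Inputs from Determination of Sample Size: 33% and 20% with an event by 4 years, 21 events, 80% power, two-sided 5%. Allocation is 1:1.

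- Hazard ratio under exponential times: ln(0.80)/ln(0.67) = 0.557, so |ln HR| = 0.585.
- Power with 21 events (Schoenfeld): Φ(√21/2 x 0.585 − 1.960) = Φ(1.340 − 1.960) = Φ(−0.620) = 0.268, about 27%.
- Events needed for 80%: 4 x (1.960 + 0.842)² / 0.585² ≈ 92.

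The stated 80% with 21 events is not reproduced.

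**All nulls true, independent tests at 5%.**

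- 18 tests: 1 − 0.95^18 = 0.603, with 18 x 0.05 = 0.9 false positives expected.
- 6 tests: 1 − 0.95^6 = 0.265.

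**All nulls true, correlated tests.** The documents give no correlations, so these are assumptions. I simulated 18 normal test statistics (6 endpoints x 3 visits, 400,000 draws per setting). The two result columns differ in the correlation between different endpoints at different visits: in one it equals the between-endpoint value, in the other it is the product of the two values.

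| Between endpoints | Within endpoint, across visits | Chance of ≥1 false positive (constant) | (product) |
|---|---|---|---|
| 0.2 | 0.6 | 50% | 51% |
| 0.2 | 0.8 | 44% | 45% |
| 0.3 | 0.7 | 45% | 46% |
| 0.5 | 0.6 | 39% | 43% |
| 0.5 | 0.8 | 35% | 37% |
| 0.7 | 0.9 | 24% | 26% |

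This gives about 35-50% for moderate assumed correlation and about 25% for very strong correlation. Even that low end is about five times 5%.

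**Some effects real.** For illustration, suppose only brain volume, spinal cord volume and serum neurofilament were null, which leaves 9 tests. Independence then gives 1 − 0.95^9 = 37%, and positive correlation would lower it.

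**The case against.** The strongest reply is that the text leaves room for an answer. The rule allows exceptions, and full detail is deferred to a SAP. No separate SAP text is among the documents, so a testing order may exist there. This stands as a qualification: the review can say only that the documents supplied give none. If the SAP holds an order, the sponsor can close the point by citing it, but until then the 5% rule is the only rule on the page.

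A second reply is that the secondary endpoints are supportive. The sample size rests on the primary alone, the secondary objective is framed as understanding the treatment effect, and no success criterion uses a secondary result. This also has force. A reader might infer that any one of 18 results below 0.05 would make the trial positive. The documents do not say so. Equally, they do not call these tests descriptive; they describe them as hypothesis tests.

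A third reply concerns size. A reader might infer from 60% that a false secondary finding is more likely than not. That needs all 18 nulls to be true and the tests to be nearly independent. Independence is not credible here: two endpoints are cumulative counts, so later visits contain earlier ones; the rest are repeated measures on the same patients; and the lesion endpoints are related to one another. A complete null is also a worst case, since the Background and Rationale report effects of ocrelizumab on MRI outcomes in established MS, although that is a different population. The reply corrects the size, but the inflation remains.

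**Conclusion.** The point holds in a limited form. Up to 18 secondary comparisons fall under a two-sided 5% rule, and nothing in the documents orders, gates, adjusts or labels them. This is a stated rule that inflates false positives, beyond a mere lack of detail.

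With all nulls true, the chance of at least one false positive is 60% under independence, about 35-50% under the moderate correlations assumed above, and about 25% under very strong correlation. It is less if some effects are real. The correlations are assumptions and the count of 18 is an upper limit. The documents do not support saying that a false finding is likely, or that the trial has no multiplicity plan anywhere, because the SAP text could not be seen.

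**What to change.** In both places where the 5% rule appears (the opening of Section 6 and Efficacy Analyses), limit it to the primary endpoint. State that secondary endpoints will be reported as estimates with confidence intervals and nominal p-values labelled descriptive. If the SAP already holds a testing order, cite it there instead.

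If formal secondary claims are wanted, name one key time point per endpoint and a fixed testing order, entered only after a significant primary, before unblinding. Each step is tested at 5%, and this holds the family-wise error for primary and secondary together at no more than 5%. The choice of visit and order is the sponsor's, with reasons given.

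Either option is about one paragraph and needs no extra patients, visits or data. The cost is in claims. Descriptive labelling gives up formal significance for every secondary endpoint. The gated sequence would give it up most of the time: with about 27% primary power at the assumed effect, the gate would stay shut in about 100% − 27% = 73% of trials. For that reason descriptive labelling is the simpler choice unless the primary power is improved.
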